8.4.6.1. Radiographic Assessment

Progression of nodal and extranodal disease should be evaluated based on the revised criteria for malignant lymphoma described in the revised International Working Group for NHL.³ The spleen is considered nodal disease.

Up to 6 measurable lymph nodes (target lesions) should be considered if the long axis is more than 1.5 cm regardless of the short axis. If a lymph node has a long axis of 1.1 to 1.5 cm, it should only be considered abnormal if its short axis is more than 1.0 cm. Lymph nodes $\leq 1.0\text{ cm} \times \leq 1.0\text{ cm}$ will not be considered as abnormal for relapse or PD. In addition, target lesions should be clearly measurable in at least 2 perpendicular dimensions and, if possible, they should be from disparate regions of the body when these areas are significantly involved. If additional lesions are present but are not included in the target lesion assessment, they can be added as nontarget lesions followed throughout the study.

Nodal progression by imaging is defined as one of the following:

- Appearance of any new lesion more than 1.5 cm in any axis or more than 1.0 cm in short axis during or at the end of therapy, even if other lesions are decreasing in size.
- At least a 50% increase from nadir in the sum of product (SPD) of any previously involved nodes.
- At least a 50% increase from nadir in the product of a single previously involved node.

Of those, regarding a lymph node with a diameter of the short axis of less than 1.0 cm at nadir, in the product of the node must increase by $\geq 50\%$ from nadir and to a size of $1.5 \times 1.5\text{ cm}$ or more than 1.5 cm in the long axis.

At least a 50% increase in the longest diameter of any single previously identified node more than 1 cm in its short axis.

Measurable extranodal disease should be assessed in a manner similar to that for nodal disease.

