8.3.1. Response Follow-up Visits (Until PD)

Participants who discontinue the study for reasons other than PD will be followed every 12 weeks (± 7 days) by clinic visit until PD or use of alternative anticancer therapy. During this period, the following procedures will be performed:

- Collect blood samples for the following laboratory tests:
 - Hematology
 - Serum protein electrophoresis (SPEP)
 - Quantitative serum IgS (IgA, IgG, and IgM)
- Overall disease assessment

- Survival status and new anticancer therapy use

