8.4. Efficacy Assessments

Response assessments will be performed using the modified consensus criteria adapted from the sixth IWWM (NCCN version 2, 2019).²⁷

Progression of nodal and extranodal disease should be evaluated based on the revised criteria for malignant lymphoma described in the revised International Working Group for NHL.³ The spleen is considered nodal disease.

Efficacy evaluation will include the following components:

- Hematologic parameters by complete blood count (CBC)
- Quantitative serum IgS (IgA, IgG, and IgM)
- Quantitative serum-M protein (SPEP)
- Qualitative serum immunofixation, if applicable
- Radiographic evaluation, if applicable
- Bone marrow aspirate and biopsy, if applicable

If disease progression is suspected solely based on the results of a single examination or a single laboratory parameter (eg, IgM), this finding should be confirmed by a subsequent evaluation at least within 4 weeks from the first finding. Additional hematologic parameters, radiographic evaluation and bone marrow biopsy should be performed at the discretion of the treating physician to confirm PD if indicated. PD is defined as one of the following:

- A $\geq 25\%$ increase in serum IgM with a total increase of at least 500 mg/dL from nadir (Confirmation of the initial IgM increase is required when IgM is sole criterion for progressive disease.)

Note: Nadir for serum IgM is defined as the lowest serum IgM value obtained at any time from baseline onwards with the exception that serum IgM levels post-plasmapheresis will not be considered for up to 35 days.

- New symptomatic disease on the basis of malignant pleural effusion, Bing Neel (WM CNS disease) syndrome, amyloidosis or light chain deposition disease, or other paraprotein mediated disorder.
- New or recurrent involvement in the bone marrow

- Measurable nodal and extranodal disease will follow the definition of nodal progression by imaging in Section 8.4.6.1
- Appearance of new splenomegaly or $\geq 50\%$ increase from nadir in enlargement of the spleen
- Appearance of new extranodal disease

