9.4.3. Secondary Endpoints

To evaluate efficacy of ibrutinib, when combined with rituximab in Japanese participants with treatment naïve or relapsed/refractory WM in terms of the following:

- Progression-free survival (PFS)
- Pharmacokinetics (PK) profile of ibrutinib and metabolite PCI-45227
- Prognostic biomarkers relative to disease and/or treatment outcomes including MYD88 and CXCR-4

Definition

PFS:

Time from the date of initial dose to the date of first documented evidence of PD, death, or date of censoring whichever occurs first, regardless of the use of subsequent antineoplastic therapy prior to documented PD or death [date of first PD or death or censoring date of initial dose+1 day]. Participants whose diseases have not progressed and who are still alive at the end of the study or clinical cutoff will be censored at the last adequate disease assessment. Participants who do not have any postbaseline disease evaluation will be censored at the date of the first dose of ibrutinib.

Analysis Methods

The all treated analysis set will be used for all secondary efficacy endpoints. The Kaplan-Meier method will be used to descriptively summarize the PFS in the all treated analysis set. Median PFS and the corresponding 95% CI will be provided if estimable with Kaplan-Meier plot.

In addition to the PK parameters described in Section 8.8.3, the plasma concentration data of ibrutinib may be used for population PK analysis. MYD88, CXCR-4, and other genetic and genomic alterations thought to be prognostic of disease and/or treatment outcome may be tested.

Safety evaluation is also a secondary endpoint for this study.

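### The only new-lesion criterion for nodal progression stops at the end of therapy, while PD is still sought and counted for PFS after ibrutinib has been stopped (minor)

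*Protocol*

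**What the plan says.** Protocol Section 8.4 lists what counts as PD. For measurable disease it hands over to the imaging section: "Measurable nodal and extranodal disease will follow the definition of nodal progression by imaging in Section 8.4.6.1". Section 8.4.6.1 introduces its list with "Nodal progression by imaging is defined as one of the following". The first item is a new lesion larger than 1.5 cm in any axis or "more than 1.0 cm in short axis during or at the end of therapy". The remaining items look back to known nodes: one is "At least a 50% increase from nadir in the sum of product (SPD) of any previously involved nodes", and the others concern a single node already involved or identified.

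The other PD items in Section 8.4 carry no time limit. They cover a rise in IgM, new symptomatic disease, marrow involvement, the spleen, and "Appearance of new extranodal disease".

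On follow-up, Sections 7 and 7.1 keep disease evaluations going after study intervention is discontinued. Section 8.3.1 sees participants who stop for reasons other than PD every 12 weeks "by clinic visit until PD or use of alternative anticancer therapy". Section 9.4.3 defines PFS as "Time from the date of initial dose to the date of first documented evidence of PD, death, or date of censoring whichever occurs first", whether or not subsequent antineoplastic therapy has been given.

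**The concern.** The period in which PD is looked for is longer than the period in which a new node can count as PD. A participant may stop ibrutinib for toxicity, enter response follow-up, and later show a new node as the only sign of relapse. On the literal text that node is not progression. The participant would then be carried as progression-free until another criterion was met, or censored if none was. Either outcome lengthens PFS. Assessors who notice the time limit and assessors who do not could also date the same case differently.

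**Working it through.** The protocol gives no figure on this point. Its one design figure is in Section 9.2: 14 participants for 80% power, with ORR 72% against a threshold of 32%. It reproduces. The smallest count whose exact two-sided 95% lower limit exceeds 32% is 9 of 14 (lower limit 35.1%). P(X ≥ 9 | n = 14, p = 0.72) = 82.8%, and at p = 0.32 the same probability is 1.3%. Sample sizes of 12 and 13 give 77.5% and 71.3%. None of this uses the new-lesion item.

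The point itself is a comparison of wording.

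1. **Can another nodal item capture a new node?** No. The items on the sum of products, the product of a single node and the longest diameter all require a node already known.

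2. **Can another PD item in Section 8.4 capture it?** Only if another sign is present: IgM, symptoms, marrow, spleen or extranodal disease. None of them names a new lymph node.

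3. **Where does therapy end?** Section 8.4.6.1 does not define it. Section 8.2 runs the treatment phase to the end-of-treatment visit, which Section 8.2.9 places 30 (+7) days after the last ibrutinib dose or before new anticancer treatment. On the generous reading the gap therefore opens after that visit, when response follow-up begins (Section 8.3).

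4. **Could a new node be seen in that period?** Section 8.3.1 lists blood tests and an overall disease assessment but no CT. The CT footnote to the Schedule of Activities allows clinically indicated assessments at any time, and Section 8.2.8 allows a suspected-PD visit at any time with CT if indicated. So it can be seen, though not on a routine follow-up scan.

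5. **What happens to PFS?** There are two routes.
   - Another criterion is met later, or the participant dies: the event is counted, but with a later date.
   - New anticancer treatment starts first: response visits end under Section 8.3.1, later PD may never be documented, and the participant may be censored at the last adequate disease assessment (Section 9.4.3).

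6. **How large is one event?** 1/14 = 7.1 percentage points. For example, with no earlier censoring, 12/14 = 85.7% free of progression becomes 13/14 = 92.9%.

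7. **Does ORR move?** Section 9.4.2 uses the best confirmed response up to the start of subsequent therapy. A node appearing after treatment does not undo a response already confirmed, so the ORR result is essentially unaffected.

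**The case against.** The strongest reply is that the list is not the whole rule. Sections 8.4 and 8.4.6.1 both say that nodal and extranodal progression should be evaluated on the cited revised lymphoma criteria. Section 8.4.6.1 also speaks of relapse alongside PD when it sets the size of an abnormal node, and IRC conventions are left to a charter. An assessor could count a later new node on that basis. The new-lesion item can also be read as making a different point, namely that a new lesion counts even when others shrink, and no sentence says that later lesions are excluded. Grammatically the time limit might attach only to the short-axis limb, although it sits more naturally with the appearance of the lesion.

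The practical reply is that exposure is small. All participants enter with measurable monoclonal IgM, and response follow-up measures IgM and SPEP every 12 weeks. The gap requires someone who stopped without PD, has not started new therapy, has an unscheduled CT, and shows a new node as the only sign after the end-of-treatment visit.

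Most of this stands and limits the weight of the point. It does not remove it. The cited criteria and the charter may permit the wider reading, but the protocol's own text, which presents its list as the definition, does not state it.

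**Conclusion.** The time limit in Section 8.4.6.1 does not agree with Sections 7, 7.1, 8.3.1 and 9.4.3. The consequence is a possible delay or omission of a PFS event, in the direction of longer PFS, for participants who stop ibrutinib without PD. PFS is secondary and summarised descriptively by Kaplan-Meier, and no success rule uses it. The severity is minor.

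Three stronger readings may be inferred, and the documents do not support them.

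- **That a given share of PFS events would be lost.** About 2 expected events by Week 57, or 6 by 30 months (14 × (1 − 0.575) = 5.95), would make one event 50% or 17% of the total. These counts borrow 79.5% at 19 months from monotherapy in relapsed/refractory disease, and 57.5% at 30 months from monotherapy in rituximab-refractory disease. Inclusion criterion 3a(2) largely screens out the second group, and neither source is the combination arm. The number stopping without PD is not given, nor is the chance that even one such relapse occurs. The 7.1 points are the size of one event if it happens, not an expected bias.
- **That the same relapse is PD or not purely by site.** The item refers to any new lesion, measurable extranodal disease is assessed similarly to nodal disease, and the spleen is classed as nodal. The contrast with the untimed extranodal and spleen items is therefore not clean.
- **That those who stop early are at higher risk of relapse.** The protocol offers no evidence for this.

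**What to change.** In the first item of the nodal-progression list in Section 8.4.6.1, replace the time limit with *at any time after the first dose, including response follow-up*. The item then agrees with Sections 8.3.1 and 9.4.3. Use the same wording in the IRC charter, so that all assessors apply one rule.

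The cost is one phrase in two documents. No scans or visits are added, and the sample size and the ORR decision rule stay as they are.

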8.4.7. Bone Marrow Sampling and Pathologic Diagnosis

Enrollment of the participants in the study will be based on local pathologic assessment and study intervention can be initiated prior to the review by the central pathologist. Central pathologic review will be performed to confirm clinicopathological diagnosis based on central pathologic assessment and histopathological confirmation of lymphoplasmacytic lymphoma (LPL), which is the underlying histology of WM. Details regarding the central pathologic review will be outlined in a separate pathology charter.

A central pathologic review will be performed for all participants. Bone marrow biopsy or bone marrow smears are necessary for bone marrow assessment.

The following material will be sent to the central pathologist:

- Stained slides from bone marrow biopsy and aspirates used for LPL/WM diagnosis (All slides including special stain and immunostaining)
- Unstained slides may be requested to be submitted if the samples need to be reviewed by unstained ones

Bone marrow samples should be obtained to confirm CR if at any time CR is suspected.

Standard clinical bone marrow assessment will be performed at the study site's local laboratory and confirmed centrally.

If a participant has not been diagnosed as WM by the central pathologist, the investigator should discuss with the medical monitor on if the participant should continue to participate in the study and whether it is appropriate to continue the study intervention.

8.5. Safety Assessments

The study will include the following evaluations of safety according to the timepoints outlined in the Section 1.3. Any clinically significant abnormalities persisting at the end of the study/early withdrawal will be followed by the investigator until resolution or until a clinically stable condition is reached.

Adverse events will be reported and followed by the investigator as specified in Section 8.6 (Adverse Events and Serious Adverse Events) and Section 10.4 (Appendix 4, Adverse Events: Definitions and Procedures for Recording, Evaluating, Follow-up, and Reporting).

Any clinically relevant changes occurring during the study must be recorded on the AE section of the eCRF.

The study will include the following evaluations of safety and tolerability according to the timepoints provided in the Section 1.3.

In addition to the Medical Monitor and investigators, the external safety monitoring committee will assess toxicity and safety at the timepoint of the prescheduled safety analyses. The

prescheduled timepoints include Week 5 data of the first 5 subjects and Week 5 data of all subjects. The charter of this committee will be prepared separately.

Details regarding the external safety monitoring committee are provided in Committees Structure in Section 10.3, Appendix 3, Regulatory, Ethical, and Study Oversight Considerations.

8.5.1. Adverse Events

All AEs will be reported from the time a signed and dated ICF is obtained until 30 days following the last dose of ibrutinib or until initiation of subsequent anticancer therapy, whichever is earlier.

Adverse events will be graded according to the NCI-CTCAE version 4.03.

8.5.1.1. Reporting of Tumor Flare

Therapy with rituximab in WM is commonly associated with a surge of IgM levels (IgM flare or tumor flare). This transient increase of IgM levels will most likely not indicate disease progression and participants may continue therapy with rituximab.

The Medical Dictionary for Regulatory Activities (MedDRA) does not support the reporting of "IgM flare" and therefore these events should be reported as an AE of 'tumor flare'. [Table 5](#) provides guidance on grading this particular event.

Table 5: Grading for Adverse Events of IgM Associated Tumor Flare

Tumor flare	
Grade 1	<25% IgM increase during rituximab therapy
Grade 2	≥25% IgM increase during rituximab therapy
Grade 3	IgM increase during rituximab therapy associated with clinical intervention (eg, plasmapheresis)
Grade 4	IgM increase during rituximab therapy associated with life-threatening consequences; urgent intervention indicated
Grade 5	Death

8.5.2. Physical Examinations

The screening, Week 1, suspected PD, EOT, and follow-up physical examination will include, at a minimum, the general appearance of the participant, height (screening only), weight, and examination per clinical practice. Review of symptoms should include inquiry of ocular symptoms; participants should be referred to an ophthalmologist for a formal examination if any eye-related symptoms of severity ≥Grade 2 are reported, and the outcome must be reported on the ophthalmologic eCRF.

A limited symptom-directed physical examination will be required after Week 1 at timepoints specified in the Section 1.3.

8.5.3. Vital Signs

Vital signs will include measurement of blood pressure, pulse rate, respiratory rate, and body temperature and will be assessed at timepoints specified in the Section 1.3.

Blood pressure and pulse rate measurements should be preceded by at least 5 minutes of rest in a quiet setting without distractions (eg, television, cell phones).

8.5.4. ECOG

The ECOG performance index is provided in Section 10.8, Appendix 8. The ECOG performance status will be assessed at timepoints specified in the Section 1.3.

8.5.5. Electrocardiograms

A single 12-lead ECG will be taken at screening. During the collection of ECGs, participants should be in a quiet setting without distractions (eg, television, cell phones). Participants should rest in a supine position for at least 5 minutes before ECG collection and should refrain from talking or moving arms or legs. If blood sampling or vital sign measurement is scheduled for the same timepoint as ECG recording, the procedures should be performed in the following order: ECGs, vital signs, blood draw.

Any clinically significant abnormalities noted at screening should be included in the medical history. Additionally, ECGs can be performed at the investigator's discretion if clinically indicated anytime during the study.

8.5.6. Clinical Safety Laboratory Assessments

Blood samples for serum chemistry, coagulation tests, and hematology and urine sample for urine pregnancy test will be collected as noted in Section 10.2, Appendix 2, Clinical Laboratory Tests. The investigator must review the laboratory results, document this review, and record any clinically relevant changes occurring during the study in the AE section of the eCRF. The laboratory reports must be filed with the source documents.

Serology

Serologies include evaluation of HIV antibody, hepatitis C antibody, HBsAb, HBsAg, and HBcAb. If HBsAb, HBcAb, HBsAg, or hepatitis C antibody is positive, then PCR to quantitate hepatitis B DNA or C RNA must be performed and must be negative prior to enrollment. Participants who are positive for Hepatitis C antibody should have documented 24 weeks of SVR in order to be eligible for the study.

Clinical and laboratory signs of active HBV infection should be closely monitored for HBV carriers or participants who have history of hepatitis B during and following study intervention, according to the Guidelines for Prevention of Immunosuppressive Therapy or Chemotherapy-Induced Reactivation of HBV Infection.¹⁹ Consultation with a hepatitis specialist is also recommended.

8.6. Adverse Events and Serious Adverse Events

Timely, accurate, and complete reporting and analysis of safety information from clinical studies are crucial for the protection of participants, investigators, and the sponsor, and are mandated by regulatory agencies worldwide. The sponsor has established Standard Operating Procedures in conformity with regulatory requirements worldwide to ensure appropriate reporting of safety information; all clinical studies conducted by the sponsor or its affiliates will be conducted in accordance with those procedures.

Adverse events will be reported by the participant (or, when appropriate, by a caregiver, surrogate, or the participant's legally acceptable representative) for the duration of the study.

Anticipated events will also be recorded and reported.

For further details on AEs and SAEs (Definitions and Classifications; Attribution Definitions; Severity Criteria; Special Reporting Situations; Procedures) as well as product quality complaints, refer to Section 10.4, Appendix 4, Adverse Events: Definitions and Procedures for Recording, Evaluating, Follow-up, and Reporting.

8.6.1. Time Period and Frequency for Collecting Adverse Event and Serious Adverse Event Information

All Adverse Events

All AEs and special reporting situations, whether serious or nonserious, will be reported from the time a signed and dated ICF is obtained until completion of the participant's last study-related procedure, which may include contact for follow-up of safety and survival. Serious AEs, including those spontaneously reported to the investigator within 30 days after the last dose of study intervention, must be reported using the Serious Adverse Event Form. The sponsor will evaluate any safety information that is spontaneously reported by an investigator beyond the time frame specified in the protocol.

Serious Adverse Events

All SAEs occurring during the study must be reported to the appropriate sponsor contact person by study-site personnel within 24 hours of their knowledge of the event.

Information regarding SAEs will be transmitted to the sponsor using the Serious Adverse Event Form and Safety Report Form of the eCRF, which must be completed and reviewed by a physician from the study site and transmitted to the sponsor within 24 hours. The initial and follow-up reports of an SAE should be transmitted electronically or by facsimile (fax).

8.6.2. Follow-up of Adverse Events and Serious Adverse Events

Adverse events, including pregnancy, will be followed by the investigator as specified in Section 10.4, Appendix 4, Adverse Events: Definitions and Procedures for Recording, Evaluating, Follow-up, and Reporting.

